Official Title: Retrieval-Based Word Learning in Developmental Language Disorder During Book Reading

Grant #: R01DC014708

NCT#: NCT06026124

Date: October 31, 2022

Definition: Type of uploaded study document. Select one.

- Study Protocol: The written description of the clinical study, including objective(s), design, and methods. It may also include relevant scientific background and statistical considerations (if the protocol document includes the statistical analysis plan, use "Study Protocol with SAP and/or ICF" option). Note: All amendments approved by a human subjects protection review board (if applicable), before the time of submission and that apply to all clinical trial Facility Locations must be included.
- Statistical Analysis Plan (SAP): The written description of the statistical considerations for analyzing the data collected in the study. Includes how data are analyzed, what specific statistical methods are used for each analysis, and how adjustments are made for testing multiple variables. If some analysis methods require critical assumptions, the written description should allow data users to understand how those assumptions were verified.

Purpose

Word learning is one of the principal weaknesses in children with developmental language disorder (DLD). Our previous work has shown that special benefits accrue when these children must frequently recall newly introduced words during the course of learning. The goal of the study is to replicate the advantage that repeated retrieval holds over simple exposure to words and to demonstrate an increase in children's absolute levels of learning by implementing retrieval practice in the context of a story book. We include typically developing peers as a comparison group.

Participant selection

Preschool children with DLD are recruited through local speech-language pathologists and preschool teachers. Children with typical language development are recruited through advertisements in parent newsletters, preschools, and community events.

For interested families, a phone interview is used to screen for the following eligibility requirements:

- 1) current age between 4;0 and 5;11 (years; months)
- 2) monolingual English speaker; or bilingual speaker with significant English exposure from birth.
- 3) no significant neurological condition or neurodevelopmental disorder (e.g. ASD).

Informed consent is obtained at the first session and eligibility testing is then completed. To be eligible, the child must:

- 1) pass a pure tone hearing screening in both ears at 20 dB at 500, 1000, 2000, and 4000 Hz
- 2) score above 75 on a test of non-verbal intelligence (*Kaufman Assessment Battery for Children – Second Edition*).
- 3) complete the *Structured Photographic Expressive Language Test – Preschool 2* and receive a standard score in the following range:
 - a. To be included in the DLD group, children had a standard score below 87. This cutoff score has been found to show good sensitivity and specificity (Greenslade et al., 2009).

- b. To be included in the TD group, children had a standard score above 87.

All children also complete the Peabody Picture Vocabulary Test – Fourth Edition. Parents complete a questionnaire that includes mother's total years of education. The PPVT standard scores and years of maternal education are both used as covariates in all statistical analyses.

For eligible children, 6 sessions are scheduled to complete the study.

Word learning procedure

In the current study, the investigators aim to increase word recall accuracy levels by embedding the same words and retrieval schedules used in earlier studies into story contexts. Two artist-illustrated stories incorporate illustrations of the unfamiliar plants and animals that served as referents of novel nouns in an earlier study. Using a within-subjects design, children will learn eight novel nouns, four embedded in each of two stories. Along with each word form, children will learn a "meaning", that is, an additional piece of semantic information about the referent. The novel words are monosyllabic (consonant-vowel-consonant) and are matched across conditions according to phonotactic probability and neighborhood density (based on Storkel & Hoover, 2010).

In order to maintain the number of word exposures used in previous studies, the stories will be presented twice during each of the two learning sessions held on consecutive days. For each story, two words will appear in the repeated spaced retrieval (RSR) condition and two words in a repeated study (RS) condition, presented in alternating order. For novel verbs in the RSR condition, the first retrieval trial is an immediate retrieval trial. After the study trial (e.g., "This is called a nepp. It's a nepp. A nepp likes worms."), the illustration is re-presented and the child is prompted to retrieve word form ("What's this called?) and word meaning ("What does it like?"). After this, all retrieval trials are "spaced", that is, they appear after the other three novel words have intervened. All retrieval trials—immediate and spaced— are directly followed by another study trial for the same novel word. The novel words in the RS condition receive the same kinds of study trials but no retrieval trials. The second day is identical to the first. Across the two days, the same number of study trials (16) are provided for the novel words in the two conditions. There are 12 retrieval trials (four immediate, eight spaced) for each novel word in the RSR condition.

Outcome measures

Primary outcome measures:

Form Recall and Meaning Recall test at 5 minutes. For each story, after the child has completed the learning session of the second day, a five-minute break is given. Then a recall test of each word form and meaning is administered. Two items for each word form and meaning are used, with the second item for each word presented only after all four words had been tested once. Prompts used for the recall items are identical to those used in the retrieval trials ("What's this called?"; "What does this one like?"). The target image of the referent (without other visual context) is taken from the story book.

Form Recall and Meaning Recall at one week. The Form and Meaning recall test is re-administered one week after the first day of learning.

Form Recognition at one week. Immediately following the one-week Recall test, a picture-pointing recognition test is administered. The illustrated image of each novel word referent is shown along with two of the other referents in the set and the child was asked, "Which one is the e.g., /nep/."

Secondary outcome measures:

Peabody Picture Vocabulary Test – Fourth Edition is completed. Standard scores are obtained and used as a covariate in all statistical analyses.

Parents complete a questionnaire that includes mother's total years of education. Years of maternal education is used as a covariate in all statistical analyses.

Scoring

Word Form Recall measure: Eight items are used for the word form recall test for each set.

Several steps are used in the scoring of children's word productions:

- 1) Productions of real words alternatives to the novel word (e.g., "cactus") are scored as incorrect.
- 2) Productions that appear to be attempts at the novel word but are not accurate are submitted to the scoring system of Edwards et al. (2004). Each consonant is awarded one point each for correct place, manner, and voicing. For vowels, one point is given for each of length, height, and backness. An additional point is credited for correct syllable shape (CVC). Given that all novel words had the syllable shape CVC, all fully adult-like pronunciations earned 10 points. For any non-adult-like production to be scored as correct, the production is required to have a higher point total than the total that would be given if the child is instead trying to produce one of the other novel words.

Meaning Recall measure: Eight items were used for the meaning recall test.

Scoring of the children's responses on the meaning recall test as correct or incorrect is straightforward, as pronunciation, even when non-adult-like, is not a factor in distinguishing among the possible meanings (e.g., grass, butterflies, rain, sun).

Form Recognition measure: Eight items were used for the form recognition test.

The child's picture pointing response is recorded at the time of test. The score for the recognition test was the number of items in which the child pointed to the correct image in the three-image array.

Data analysis plan

Mixed-effects models will be used to evaluate the children's recall and recognition of the novel words. Models will be run with and without the covariates of PPVT-4 and maternal education in years. The number of items correct is the outcome measure for each analysis. The form and meaning recall test is administered five minutes after the learning period and one week later. For this test, diagnostic group (DLD, TD) is a between-participants variable and learning condition (RSR, repeated study), time (five minutes, one week) are within-participants variables. The word recognition test is administered only at the one-week mark and therefore does not include time as a variable. Random slopes for learning condition, item type, and time will be included when they do not approach zero.

Main-effects models and full factorial models with all possible interactions will be tested hierarchically. The main-effects models will be run initially with no interactions to provide a baseline of each model variable. Statistically significant interactions will be analyzed and relevant simple effects are reported. Effect sizes will be presented as partially standardized beta coefficients (b_{std}). To account for non-normal error terms, we will use boot-strapped standard errors with 1,000 replicates. Stata Version 18.0 (StataCorp, 2023) will be used for the mixed-effect model analyses.

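### No planned model includes age, so any DLD–TD age difference within the 4;0 to 5;11 band would carry into the group contrast on raw scores

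*Combined protocol and SAP*

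**What the plan says.** Under Data analysis plan, "diagnostic group (DLD, TD) is a between-participants variable", and learning condition and (for recall) time are the within-child factors. Main-effects models come first, so a DLD–TD level estimate will be produced; then "full factorial models with all possible interactions will be tested hierarchically". On the outcome scale: "The number of items correct is the outcome measure for each analysis".

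On covariates, the Data analysis plan says "Models will be run with and without the covariates of PPVT-4 and maternal education in years". Participant selection says "The PPVT standard scores and years of maternal education are both used as covariates in all statistical analyses", and the secondary outcome section repeats for the PPVT-4 that "Standard scores are obtained and used as a covariate in all statistical analyses". Whether the covariates are in all models or only in one of two versions, the list is the same two variables.

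Age appears once, as a phone-screen eligibility range of 4;0 to 5;11 that applies to both groups. The groups are set by a cut-off on an expressive language test: "To be included in the DLD group, children had a standard score below 87", with TD children above that value. The only matching described is of the novel words across conditions. Children with DLD come through speech-language pathologists and preschool teachers. TD children come through advertisements, including in preschools.

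**The concern.** A standard score compares a child with others of the same age, so by construction it carries little or no information on age itself. Adjusting for the PPVT-4 standard score therefore does not adjust for age, and defining the groups by a standard score does not equalise age. The outcome is different in kind: a raw count, which may well rise over a two-year span of the preschool years.

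Diagnostic group is observed, not assigned. If one group were older, part of the DLD–TD difference would reflect age rather than diagnosis. An older DLD group would make the deficit look smaller, and a younger one would make it look larger. No planned version of the model would separate the two, and the plan does not say that age will be reported by group, so a reader could not judge it.

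Only this level contrast is exposed. In the comparison of repeated spaced retrieval (RSR) with repeated study (RS), each child is his or her own control and age cancels. The group-by-condition interaction would be affected only if age changed the size of the retrieval benefit, and the documents give no evidence of that.

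**Working it through.** The documents give no sample size, power, score SD, age distribution or age–score correlation, so there is no planned figure to reproduce. What follows is an illustration.

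**From the documents.** Age range 4;0 to 5;11, taken as 48 to 72 months (a 24-month band); raw-count outcome; covariates PPVT-4 standard score and maternal education; two non-randomised groups.

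**Assumed.** 20 children per group; within-group age–score correlation r = 0.1, 0.3 or 0.5; a systematic gap d of 1, 2 or 3 months; ages spread evenly within each group over a window of 24 − d months (for d = 3: 48–69 and 51–72); one score per child; no true group effect. For the covariate-adjusted model, r means the partial correlation after PPVT-4 and maternal education.

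**Shift in the group contrast without age in the model.**
- SD of age = (24 − d)/√12, which is 6.64, 6.35 and 6.06 months for d = 1, 2 and 3.
- Shift in score SDs = r × d / SD of age. For d = 3 and r = 0.3: 0.3 × 3 / 6.06 = 0.148.
- Standard error of the contrast = √(2/20) = 0.316 SD. The 95% interval half-width is 2.024 × 0.316 = 0.640 SD.
- Rejection of a true null is from the noncentral t distribution, 38 degrees of freedom, noncentrality shift/0.316.

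| Gap | Shift (SD), r = 0.1 / 0.3 / 0.5 | Rejection at 5%, r = 0.1 / 0.3 / 0.5 |
|---|---|---|
| 1 month | 0.015 / 0.045 / 0.075 | 5.0% / 5.2% / 5.6% |
| 2 months | 0.031 / 0.094 / 0.157 | 5.1% / 6.0% / 7.7% |
| 3 months | 0.049 / 0.148 / 0.247 | 5.3% / 7.4% / 11.9% |

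At r = 0.3 the shift is 7%, 15% and 23% of the interval half-width (0.045, 0.094 and 0.148 over 0.640).

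**Effect of adding age, 3-month gap (simulation, 20,000 runs).** Without age the mean shift was 0.047 / 0.147 / 0.245 SD and rejection 5.0% / 7.3% / 12.0%, in line with the table. With age the mean shift was within 0.003 SD of zero and rejection was 4.9% / 5.0% / 5.4%.

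**Price of adding age.** The ratio of standard errors, with age over without, is √[(1 − r²)(1 + 1/(2n − 4) + (n/2)(d/SD)²/(2n − 4))].
- n = 20, no gap: √[(1 − r²)(1 + 1/36)] = 1.009 / 0.967 / 0.878.
- n = 20, 3-month gap: (3/6.06)² = 0.245, so the second bracket is 1 + 0.028 + 10 × 0.245/36 = 1.096, and the ratio is 1.042 / 0.999 / 0.907.
- Break-even r is about 0.16 with no gap and 0.30 with the 3-month gap. Below that, age adds no precision.
- Root mean squared error with the 3-month gap (40,000 runs): 0.319 / 0.348 / 0.403 without age and 0.328 / 0.315 / 0.288 with it. At r = 0.1 adjustment is slightly worse; at 0.3 and 0.5 it is better.

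**Do the planned covariates absorb the gap?** A separate simulation (2,000 runs, 20 per group) used scores of 0 to 8, because each condition has 2 words × 2 stories × 2 items = 8 recall items per time point. It assumed a score SD of about 2 items, and PPVT-4 standard score and maternal education unrelated to age. With r = 0.3 and a 4-month gap, the spurious difference was 0.33 items with group alone, 0.32 with the two planned covariates, and −0.01 once age was added. The two age windows were slid apart here, so some simulated ages lie slightly outside the eligible band. The result is used only to show that the planned covariates do not stand in for age under these assumptions.

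**The case against.** The strongest reply is that nothing in the documents points to an age difference. Both groups face the same age band, the TD children are described as peers, and both are partly reached through preschools. A reader might infer from the partly different recruitment channels that the groups will differ in age. The documents do not support that, since nothing in them links channel to age. This part of the reply stands, and the point is conditional. A chance difference in age is not at issue either: it is already reflected in the standard error.

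Second, the shared band limits how far apart the groups can be, so it would be too strong to call the contrast unprotected. That also stands. The limit is loose, though: a gap of 1 to 3 months fits easily inside 24.

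Third, the 12% rejection rate needs the largest gap and the largest correlation considered; gaps of 1 or 2 months give 5% to 8%. A true null is also not the working hypothesis, because the Purpose section presents word learning as a weakness in DLD. The practical effect would be a modest change in the size of an expected deficit. This is fair, and is why the shift is also shown against the interval half-width.

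Fourth, adding age is not uniformly better: at r = 0.1 it costs a little precision. That stands as a small price.

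What the reply does not answer is that no passage prevents, adjusts for or promises to report an age gap. Maternal education, like age, cancels from the within-child contrast, so listing it suggests that the plan does mean to adjust differences between children.

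**Conclusion.** The point holds as a conditional and modest one, worth considering. Every planned model for the raw scores leaves chronological age out, so a systematic age difference between the groups would carry into the DLD–TD level contrast. Under the assumed values (20 per group, 1- to 3-month gap, r of 0.1 to 0.5) the shift is about 0.02 to 0.25 SD, with about 5% to 12% rejection of a true null. All three inputs are assumptions, because the documents give none of them.

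A reader might go further and conclude that the retrieval finding is at risk. It is not, since RSR and RS are compared within each child. Nor can one conclude that the group contrast is biased, since no age difference is shown.

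**What to change.** In the Data analysis plan:

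- Add age in months, centred, to the covariate-adjusted recall and recognition models, as a child-level main effect outside the factorial interactions.
- Keep the version without covariates as planned.
- State in advance that the age-adjusted model is the one used to interpret the DLD–TD level contrast, so that the change adds no analytic choice.
- Report the mean and SD of age by diagnostic group.

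No further age-only model is needed. Whether the PPVT-4, itself a language measure, belongs in a model comparing language-defined groups is a separate question. If children are in fact matched on age, stating the rule would largely answer the point.

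The cost is about two sentences, one model term and one descriptive row, using a value already asked at screening. The downsides are one degree of freedom, a linear age slope assumed common to both groups, and, if age is nearly unrelated to the score (r = 0.1, 20 per group), a standard error larger by about 1% when the groups are age-balanced and about 4% with a 3-month gap.

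### Does the undefined term 'item type' in the random-slope sentence leave the recall analysis open?

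*Combined protocol and SAP*

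**What the plan says.** The Data analysis plan describes one form and meaning recall test, given at five minutes and at one week. For that test, "diagnostic group (DLD, TD) is a between-participants variable and learning condition (RSR, repeated study), time (five minutes, one week) are within-participants variables". The outcome of each analysis is the number of items correct. Interactions are handled as follows: "Main-effects models and full factorial models with all possible interactions will be tested hierarchically". Significant interactions are then followed by simple effects. The sentence on random effects reads: "Random slopes for learning condition, item type, and time will be included when they do not approach zero". That is the only appearance of *item type* in the document.

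Of the recognition model the same section says: "The word recognition test is administered only at the one-week mark and therefore does not include time as a variable".

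Elsewhere, Outcome measures treats form and meaning recall as one test: "The Form and Meaning recall test is re-administered one week after the first day of learning". Scoring describes them one after the other: "Word Form Recall measure: Eight items are used for the word form recall test for each set" and "Meaning Recall measure: Eight items were used for the meaning recall test".

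**The concern.** A random slope belongs to a variable in the model, and the listed recall model has no *item type*. If the term means form versus meaning, there are two ways to complete the plan:

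- **Joint model.** Item type is a fourth factor, with one overall RSR effect on recall.
- **Separate models.** Form and meaning are analysed apart, giving two RSR effects. The item-type slope then cannot be estimated, because the factor is constant within each model.

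The plan runs full factorials, so the factor list decides which tests are done. Form and meaning recall are both primary measures and no multiplicity adjustment is stated. A reader could fairly worry that the number of tests behind a claim that RSR beats RS on recall is not fixed in advance, and that the same data might support different conclusions.

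**Working it through.** **1. Which reading does the text support?**

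| Place | Content | Points to |
|---|---|---|
| Data analysis plan | A single form and meaning recall test, with one set of variables given for it | Joint |
| Data analysis plan | Item-type slope listed between condition and time | Joint |
| Data analysis plan | Within-participants list has a comma where a conjunction or a third member is expected | Joint, member dropped |
| Outcome measures | Form and meaning recall named together at each time point | Joint |
| Scoring | Separate entries for form and meaning | Neither: pronunciation matters for form only, so two scoring rules are needed in any case |
| Data analysis plan, recognition sentence | Only time is named as absent, although a form-only test would lose a form/meaning factor too | Separate, weakly: the sentence explains a timing fact |

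A third reading is first versus second test item, since Outcome measures says "Two items for each word form and meaning are used". It is strained: the outcome is a count of items correct, and no stated aim concerns item order.

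**2. Item counts agree under either completion.** Per story, 4 words × 2 items = 8 form items and 8 meaning items. Per condition, 2 words × 2 items × 2 stories = 8 for each of form and meaning.

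**3. Number of tests.** A full factorial in k two-level factors has 2^k − 1 terms, of which k are main effects.

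- Separate (k = 3): 7 terms, so 7 − 3 = 4 interactions in each of two models.
- Joint (k = 4): 15 terms, so 15 − 4 = 11 interactions, four of which contain both condition and item type.

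**4. Size of the difference.** The documents give no sample size, SD or effect size, so every input is assumed: 40 children in two equal groups, residual SD 1, condition-slope SD 0.5, two-sided 0.05, and an extra child-level SD s of 0 or 1 in the form-minus-meaning RSR difference.

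Chance of any RSR claim on recall when there is no effect (simulated):

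- Joint, averaged effect alone: about 5%.
- Joint, with the planned simple effects after a significant condition × item type term: 7.6% (s = 0) to 8.3% (s = 1).
- Separate, form or meaning: 9.6% with uncorrelated differences (theory for independent tests: 1 − 0.95² = 9.75%), and 7.8% at correlation 0.8.

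The plan does call for simple effects, so the fair comparison is 7.6–8.3% against 9.6%. The gap is 9.6 − 8.3 = 1.3 to 9.6 − 7.6 = 2.0 points.

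**5. Power.** The per-child variance of the RSR − RS difference is 0.5² + 2/4 = 0.75 averaged over form and meaning. For form alone it is 0.5² + 2/2 + (s/2)², which is 1.25 (s = 0) or 1.50 (s = 1). The standard error is √(variance/40), with 38 df.

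| True benefit (items) | Averaged test | Form test at 0.05 | Form test at 0.025 |
|---|---|---|---|
| Form 0.5, meaning 0 | 43% | 71–79% | 60–69% |
| Both 0.5 | 94% | 71–79% | 60–69% |

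The averaged test is stronger when both outcomes benefit, and the form test when only form does. For any RSR claim on recall at s = 0, joint (with simple effects) against separate is 73% against 80% with a form-only benefit, and 95% against 94% when both benefit.

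**The case for a change.** The best case for a change is that these are primary outcomes, the repair is two or three sentences, and the two completions can disagree. If a joint averaged effect is read as a verdict on form and on meaning whenever no condition × item type term is significant, the completions differ on at least one outcome in 21–28% of simulated trials (0.5-item benefit on form only) or 25–35% (on both), at 40 children.

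Little of this survives. The reading rule is not in the plan, and an averaged main effect makes no claim about either outcome alone. The simulated settings also imply form–meaning correlations of only 0.25/1.25 = 0.2 (s = 0) and 0 (s = 1). Raising the condition-slope SD to 2 gives 4/5 = 0.8, and disagreement falls to 5.7% and 13.4%, partly because power is lower there. With a 1-item form-only benefit it is 0.5–4%. A figure of 11.4% for false claims can be reached by choosing among the three tests after seeing the data, but nothing in the documents suggests that.

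Two things do stand. The term is undefined, and the text alone does not exclude separate models. The lack of a stated adjustment is also real, but it applies under either completion and extends to Form Recognition, which is a primary outcome too. Defining *item type* would not resolve it.

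**Conclusion.** The observation about the text is correct, but no change follows. *Item type* is almost certainly the form/meaning factor of a joint recall model, left out of one list. An analyst would either enter it as a within-participants factor or, if form and meaning were modelled separately, drop the slope because it could not be estimated. Neither choice biases the RSR − RS comparison. On the assumed inputs, the false-claim rates differ by about 1 to 2 points, and the power comparison favours neither completion throughout, so imposing one brings no clear gain. The sizes depend on the assumed sample size, SDs, effects and correlations. The reading of the text and the absence of bias do not. If the section is revised for other reasons, a few words naming the levels of *item type* would tidy it.

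### Recall at five minutes and at one week are separate primary outcomes, but the analysis plan does not commit to reporting the RSR-RS effect at each time

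*Combined protocol and SAP*

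**What the plan says.** Under Primary outcome measures, recall appears as two entries. The first is "Form Recall and Meaning Recall test at 5 minutes". The second is "Form Recall and Meaning Recall at one week. The Form and Meaning recall test is re-administered one week after the first day of learning". The remaining primary outcome is a picture-pointing recognition test, given once, at the later visit.

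The Data analysis plan treats recall as one test given twice: "learning condition (RSR, repeated study), time (five minutes, one week) are within-participants variables", with diagnostic group between participants. Two kinds of model follow: "Main-effects models and full factorial models with all possible interactions will be tested hierarchically". On the first kind, "The main-effects models will be run initially with no interactions to provide a baseline of each model variable". On follow-up, "Statistically significant interactions will be analyzed and relevant simple effects are reported".

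For recognition, "The word recognition test is administered only at the one-week mark and therefore does not include time as a variable".

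No RSR-RS contrast at five minutes or at one week is named as the result for the corresponding primary outcome, and no separate model per time point is planned.

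**The concern.** Five-minute recall reflects learning just after training; one-week recall reflects retention. Listing them separately implies that each will have its own answer. The plan guarantees only the time-averaged answer, and the averaged score is not itself a listed outcome. The answer at each time is tied to an interaction test.

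That test is a weak basis for deciding what to report. It may have low power, and failing to reject it is not evidence that the retrieval advantage is the same at both times. If the advantage shrinks over the week, the averaged coefficient is too large for one-week recall and too small for five-minute recall. A significant averaged effect could then be read as success on both outcomes when the one-week data alone would not show it.

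**Working it through.** The plan states no sample size, alpha, SD or expected effect, so it has no figure to reproduce. The check has three parts.

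**1. What each planned model gives.** Without a condition-by-time term, and with balanced data, the condition coefficient is the mean of the two time-specific effects. Simulated data for 40 children (condition and time within child, group between) confirm this:

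- main-effects model: one coefficient, 0.969;
- full factorial model: 1.123 at five minutes and 0.816 at one week;
- (1.123 + 0.816)/2 = 0.969.

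The factorial model returns both effects whatever the interaction p-value. Only their follow-up and reporting depends on significance.

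**2. Illustration in items correct.**

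From the documents: two stories × two words per condition × two test items per word = 8 items per condition at each time.

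Assumed: n = 40 children; the within-child RSR-RS difference has SD s = 2.0 at each time, with correlation ρ = 0.5 between times; true effects 1.25 (five minutes) and 0.5 (one week); two-sided 0.05.

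- Averaged effect: (1.25 + 0.5)/2 = 0.875. Against one week, 0.875/0.5 = 1.75 (75% too large). Against five minutes, 0.875/1.25 = 0.70 (30% too small).
- SE, averaged: s√((1+ρ)/(2n)) = 2.0 × √(1.5/80) = 0.274.
- SE, condition by time: s√(2(1−ρ)/n) = 2.0 × √(1/40) = 0.316.
- SE, single time: s/√n = 2.0/√40 = 0.316.
- Single time against averaged: 0.316/0.274 = 1.15.

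Simulation of 40,000 trials per setting, with paired t-tests:

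| Setting (effects 1.25/0.5, n = 40) | Averaged significant, interaction not | Of all trials: as before, and one week alone not significant |
|---|---|---|
| SD 2.0, ρ = 0.3 | 46% | 21% |
| SD 2.0, ρ = 0.5 | 32% | 13% |
| SD 2.0, ρ = 0.7 | about 12% | 4% |
| SD 2.0, ρ = 0.8 | 4% | 1% |
| SD 1.5, ρ = 0.5 | 13% | 2% |

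In the ρ = 0.5, SD 2.0 row, the averaged test is significant in 88% of trials and the interaction in about 64%. Over n = 30 to 60 in that setting, the 32% runs from 37% to 18%.

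A milder decline, 1.5 to 1.0 items (n = 40, SD 2.0, ρ = 0.5), gives 66% and 4%. Separate results are then often missing, but the averaged effect seldom misleads about one week.

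**3. Power of the interaction test in SD units** (normal approximation; n = 20 to 60, ρ = 0.3 to 0.7).

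- Effects 0.6s and 0.3s: the condition-by-time test is significant with probability 21% to 85%. At n = 30, ρ = 0.5 it is 38%, so 62% of such trials would not trigger follow-up through this interaction, although the one-week effect is half the five-minute effect.
- Effects 0.6s and 0: 62% to nearly 100%.
- Equal effects of 0.6s: 5%. The average is then correct for both times, but the separate results would still usually go unreported under the rule.

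Parts 2 and 3 model only the condition-by-time trigger and omit diagnostic group.

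**The case against.** A reader might infer that the RSR effect at each time is estimated only if condition by time is significant. The documents do not support that. The sentence about starting without interactions covers the first step only; the sentence before it plans full factorial models, which contain the condition-by-time term.

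A reader might also take condition by time to be the only route to a time-specific result. The follow-up sentence refers to significant interactions in general, so group by condition by time could lead there too. Nor does the plan say in terms that simple effects are withheld otherwise; that is the natural reading, but an inference. The illustrated rates of missing results are therefore, if anything, too high.

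A third tempting reading is that the model is wrong for the endpoints. It is not. A repeated-measures factorial analysis is conventional, the same test is given at both times, and the Purpose section states a general advantage of retrieval over exposure with no time-specific hypothesis.

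Finally, the percentages rest on assumed inputs and move widely with the correlation and SD.

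All of this stands. It narrows the point to pre-specification and reporting but does not remove it: nothing in the plan commits to a result for each recall outcome it calls primary.

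**Conclusion.** The point holds as a gap in pre-specification, for form and meaning recall only. The main-effects model averages the condition effect over time. The factorial model can separate the times, but reporting at each time is tied to interaction tests that may have low power. Following the stated rule can leave a primary recall outcome without its own RSR-RS result.

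The size is illustrative. In the 40-child example (SD 2.0, effects 1.25 and 0.5 items), the averaged effect is significant without the interaction in about 32% of trials at correlation 0.5, with a range of about 4% to 46% over correlations 0.8 to 0.3. In about 13% of trials (range about 1% to 21%), the one-week contrast is also non-significant. These are not estimates for this trial, and the 75% overstatement at one week follows from the assumed decline. The change is worth making because it is cheap; the gap does not undermine the design.

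**What to change.** In the Data analysis plan, for form recall and for meaning recall:

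- pre-specify the RSR-RS contrast at five minutes and at one week from the planned full factorial model, each with a confidence interval, and say whether it is averaged over the DLD and TD groups or given by group;
- report both whether or not any interaction is significant, as the results for the listed primary outcomes;
- keep the time-averaged effect as a supporting summary and the condition-by-time term as the test of change over the week;
- state how multiplicity is handled across the primary contrasts: four for recall (two measures × two times) if averaged over groups, plus recognition.

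If the sponsor's real target is the time-averaged effect, the alternative is to name that as the primary quantity and amend the outcome list to match.

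The cost is a few sentences and some post-estimation contrasts from a model already planned, with no new data. There are two downsides: each time-specific contrast has a larger SE than the averaged one (about 15% at an assumed correlation of 0.5), and there are more primary tests to account for.
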